## 1. Project Summary

Lymphedema is an incurable and chronic condition where damage or blockage to the lymphatic system leads to swelling, pain, numbness, recurring infections, and fibrosis. Women diagnosed with breast cancer undergoing axillary lymph node surgery may develop lymphedema due to damage or blockage of the lymphatic vessels that drain the arm. Rates range from 6-46% depending on the extent of axillary surgery.

Axillary reverse mapping (ARM) is a technique performed by breast surgical oncologists as a way to potentially decrease the risk of lymphedema from axillary surgeries. ARM identifies the lymphatic channels draining from the arm during primary breast tumor resection and axillary lymph node surgery, thereby differentiating those draining the breast vs those draining the arm. To date, ARM is most commonly performed using either a blue dye or immunofluorescence. At the time of axillary node surgery, the dye is injected in the subcutaneous fat in the upper arm, resulting in enhanced visualization of lymphatics. These lymphatics may then be spared, reducing the risk of lymphedema. However, significant limitations to the use of blue dye in lymphatic mapping exist. To visualize blue dye, the surgeon must dissect through the soft tissue directly to a blue lymphatic, which can result in variable success in identifying the ARM nodes and/or lymphatics, as well as a persistent blue stain at the site of injection.

Compared to blue dye, fluorescence-guided surgery (FGS) with indocyanine green (ICG) dye represents an opportunity to greatly enhance the potential of the ARM procedure to increase the surgeon's confidence in identifying the lymphatic architecture before focusing on the operative field. FGS allows the surgeon to visualize lymphatics without the need to dissect directly to the lymphatic channels; rather than directly exposing the lymphatics with surgical dissection, the lymphatics can be viewed on the imaging platform. In one prospective study evaluating the ARM procedure, patients underwent injection with both isosulfan blue dye and ICG. This study reported that blue dye and ICG identified a similar number of lymph nodes but ICG identified greater number of lymphatics draining the arm. However, challenges also exist in the use of FGS with ICG for ARM surgery. Commercially available imaging platforms to support fluorescence-guided surgery do not work with ambient lighting. Ambient room light contamination of near-infrared fluorescence (NIRF) signal emitted from fluorescence dye injected into the patient typically requires ambient lights in the operating room to be dimmed or turned off to capture the fluorescence images. This limits surgeons' ability to use FGS in real-time. Some FGS imagers attempt to compensate for ambient light through background subtraction, which leads to reduced image quality due to dynamic range compression, reduced sensitivity due to shorter effective collection times, and added display latency.

In this proposal, we will assess the feasibility of using the Asimov Imaging Platform for fluorescence-guided surgery along with ICG in the operating room for the ARM procedure. FGS with ICG is an acceptable approach to performing the ARM procedure nationally and internationally. Theoretical benefits to the Asimov Imaging Platform exist, specifically that it can be used without altering external (i.e., room) light functionality or levels, which will enable real-time visualization of lymphatics using both fluorescence and familiar anatomical reference points to support ARM.

The objective of this study is to assess the feasibility of using fluorescence-guided surgery with ICG dye through the Asimov Imaging Platform for the axillary reverse mapping procedure. We will use blue dye to guide clinical decision making. We will compare the ICG fluorescence findings (research) with the blue dye (standard of care). Nationally and internationally, both blue dye and FGS with ICG dye are used. In this study, we are specifically evaluating the feasibility of the Asimov Imaging Platform for fluorescence-guided surgery with ICG dye.

## 2. Background and Significance

[figure not shown]
Breast cancer is the most common cancer among women globally, with more than 2 million new cases diagnosed annually. In the United States, more than 250,000 women a year are diagnosed with breast cancer. Surgery is central to cancer treatment, with more than 90% of these patients undergoing surgery for tumor resection, mastectomy, or breast reconstruction. Survival of breast cancer patients has increased substantially as a result of improved, multidisciplinary treatment approaches which means that survivors are also living longer with any morbidity resulting from treatment, including lymphedema.

Lymphedema is an incurable and chronic condition where damage or blockage to the lymphatic system leads to swelling, pain, numbness, heaviness, recurring infections, and fibrosis. Women undergoing axillary lymph node surgery may develop lymphedema due to damage or blockage of the lymphatic vessels that drain the arm. In affected breast cancer patients, lymphedema often manifests in the arm weeks to years after the removal of the primary tumor or radiation therapy. Rates of lymphedema range from 6%-46%, depending on the extent of axillary surgery. A recent systematic review of 72 clinical studies (N=29,612 women) revealed that approximately 1 in 5 women who survive breast cancer will develop arm lymphedema. Not only does lymphedema reduce quality of life, it has long been a feared complication of surgical cancer treatment impacting survivorship: fear stems from a patient's concerns regarding the chronic, progressive nature of the condition and the clinician's relative inability to predict or prevent it from occurring. Further, associated per patient costs range from \$3000 to \$16,000 annually.

Because lymphedema may result from iatrogenic damage to upper limb lymphatics during axillary lymph node surgery, identification and preservation of arm lymphatics decreases the likelihood of lymphatic disruption during axillary lymph node surgery, leading to a lower incidence of upper limb lymphedema. Axillary surgery has historically consisted of an axillary lymph node dissection (ALND) where between 15 to 20 lymph nodes were removed from the axilla. Lymphedema rates for an ALND range between 20% and 40% in published studies. Because of the associated morbidity rates, this procedure is now only performed for patients with confirmed axillary disease. For women with clinically negative axillary lymph nodes, axillary staging is performed with a sentinel lymph node (SLN) biopsy. The SLN biopsy procedure involves pre-operative mapping of the lymphatics to identify one or two lymph nodes where the breast would drain to first if the disease had spread. These lymph nodes are then removed through a small incision. Lymphedema rates are lower with this procedure, but still range from 5% to 7% in prospective randomized controlled trials.

Axillary reverse mapping (ARM) is a technique performed by breast surgical oncologists as a way to potentially improve the quality of axillary surgeries. As shown in **Figure 1**, ARM is utilized to identify the lymphatic channels from the arm and differentiate them from the breast lymphatics during primary tumor resection and axillary lymph node surgery. To date, ARM is most commonly performed using a blue dye or immunofluorescence, which is injected in the subcutaneous fat in the upper arm, resulting in enhanced visualization of lymphatics at the time of axillary node surgery. Studies have shown that lymphedema rates decrease three-fold when using ARM.

Significant limitations to the use of blue dye in lymphatic mapping exist, including its low optical depth penetration, insufficient identification rates of the ARM nodes and/or lymphatics, as well as a persistent blue stain at the site of injection. Most importantly, the blue lymphatics can only be identified with direct dissection onto the lymphatic, something that is challenging when using a small incision (as for a SLN biopsy) or in obese patients (where the blue lymphatics are deeper and surrounded by adipose tissue making them more difficult to identify). Finally, the blue lymphatics from the arm may actually drain outside the operative field and never be visualized due to its low visual penetration depth; in these situations, the breast surgeon is less confident whether the blue lymphatic was inadvertently divided, or whether it was tracking along a different route.

**Figure 1. Axillary reverse mapping (ARM).**

(A) Sentinel lymph nodes and typical lymphatic drainage patterns from the breast are identified (green). Lymphography with (B) blue dye is challenging due to the non-specific binding to the lymphatics (blue) and poor signal retention. (C) Lymphatic vessels are shown clearly with ICG lymphography (white). Although ICG easily highlights large lymphatic vessels, small and critical lymphatic vessels, which can be as small as 1 mm in diameter, are unable to be seen. *The clinical need in spatial and sensitivity resolution highlights the need for improved FGS imaging systems.*

Fluorescence-guided surgery (FGS) with indocyanine green (ICG) represents an opportunity to greatly enhance the potential of the ARM procedure to increase the surgeon's confidence in identifying the lymphatic architecture before focusing on the operative field. As ICG has shown to offer deeper optical penetration than blue dye with ability to detect lymphatic channels located up to 2 cm deep, surgeons can follow the route of drainage from the injection site through lymphatic vessels to preserve its patency.

In this proposal, we will use the Asimov Imaging Platform for fluorescence-guided surgery in the operating room. The Asimov can be used without altering external (i.e., room) light functionality or levels. This will enable real-time visualization of lymphatics to support ARM and would represent a significance advancement.

Technical gaps in the literature limit our understanding of ICG fluorescence for ARM that impact implementation of this approach within the clinical workflow. Specifically, we need to quantify the critical image acquisition parameters that provide 1) surgeons' detection contrast (CNR) of post-injection time and 2) fluorescence signal retention of lymphatic vessels. The post-injection time is valuable for elucidating the optimal clinical workflow. Although some studies inject more than two hours before surgery, others inject immediately before the axillary surgery. In healthy patients, ICG typically reaches the nearest draining lymph node within 15 minutes, but because lymphatic clearance and backflow are dependent on the damage to vasculature, the optimal post-injection imaging time point will vary depending on the severity of damage to lymphatic vasculature. Thus, the clinical workflow is difficult to establish and optimize.

The fluorescence signal retention is necessary to enable surgeons to identify and be able to see these lymphatic vessels during surgery. Previous studies have not provided these parameters, largely due to inherent limitations in quantification capabilities of existing fluorescence imaging technology. Furthermore, existing fluorescence imaging technology does not provide fluorescence overlay on the white light reflectance image. This visualization is critical to provide surgeons with familiar anatomical reference points seen with white light that are further enhanced with fluorescence. This fluorescence illuminates the lymphatic flow and its location to support appropriate navigation around critical structures to preserve patency when possible.

### 3. Study Objective and Specific Aims

Specific Aim 1: To determine the feasibility of using ICG fluorescence through the Asimov Imaging Platform for axillary reverse mapping by comparing lymphatic visualization using blue dye (standard of care) versus ICG fluorescence imaging.

Specific Aim 2: To define optimal image acquisition parameters of using ICG fluorescence through the Asimov Imaging Platform for axillary reverse mapping to inform the clinical workflow.

- 2a. To define dynamic range of ICG fluorescence signal in lymphatic vessels and background.
- 2b. To assess image contrast as a function of ICG dose and time post-injection.

## **4. Research Design and Methods**

### **4.1. Study Overview**

Lymphatic drainage from the upper arm is often different from that of the breast, allowing safe removal of only the lymphatics of the breast and protection of the lymphatic channels draining the upper extremity during axillary dissection (AD) or sentinel lymph node (SLN) biopsy, thereby reducing the risk of arm lymphedema. In this prospective study, breast cancer patients undergoing SLN biopsy (n=0-20) or axillary lymph node dissection (n=0-15) will be enrolled to undergo axillary reverse mapping (ARM) using isosulfan blue dye. Patients will also receive ICG injection with visualization through the Asimov Imaging Platform to allow comparison of blue dye versus ICG lymphatic identification.

We will also define optimal image acquisition parameters of using ICG fluorescence through the Asimov Imaging Platform for ARM. We will use quantitative fluorescence to define optimal image acquisition parameters. In order to elucidate injection technique superiority, the critical image acquisition parameters that provide surgeons detectable contrast (CNR) of post-injection time, and fluorescence signal retention of lymphatic vessels will be measured. The post-injection time is valuable for elucidating the optimal clinical workflow. The fluorescence signal retention is necessary to enable surgeons to identify and be able to see these lymphatic vessels during surgery.

### **4.2. Selection of Participants**

Inclusion criteria:

- $\geq 18$  years of age
- Diagnosis of breast cancer requiring surgical lymph node evaluation either by sentinel lymph node biopsy or axillary lymph node dissection
- Surgery at University of Wisconsin Hospital and Clinic

Exclusion criteria:

- Pregnant or breast feeding
- Unable to provide informed consent
- Allergy to indocyanine green
- Patients with clinically positive lymph nodes undergoing sentinel lymph node biopsy, with or without axillary lymph node dissection, after neoadjuvant chemotherapy

### **4.3 Screening and recruitment:**

Patients being cared for by [name] within the UW Breast Center will be eligible for consideration. [name] will identify eligible patients from her clinical practice and introduce the study to them at the time of their clinic visit. A clinical research coordinator will then discuss the study in detail and obtain informed consent. Participants will have sufficient time to consider participating in this study.

### **4.4. Consent Process**

The consent process will occur at the Breast Center. Subjects will be consented in a closed private room by a member of the study team. As much time as needed will be given for potential subjects to decide whether or not to participate in this study. Subjects will receive a copy of the consent form and

will be given contact information for study coordinator and PI for any additional questions. Subjects will be informed that they are not obligated to participate in the study.

#### **4.5. Study procedures:**

##### Standard of Care Procedures:

Axillary surgery: Axillary lymph node dissection or sentinel lymph node biopsy will be performed as indicated by the patient's clinical history. For patients enrolled in the study, sentinel lymph node mapping and biopsy will be performed using technetium-99m sulfur colloid only (no injection of isosulfan blue dye in the breast), which is an acceptable standard of care. The participating surgeon will otherwise follow their usual practice for performing these routine procedures.

Axillary reverse mapping: Axillary reverse mapping is an acceptable standard of care and has been used internationally (including at the UWCHC) to reduce the risk of lymphedema for women undergoing axillary surgery. ARM is also currently being studied in an NCI funded trial to determine the extent to which ARM reduces lymphedema risk (NCT039270127). We will use the ARM procedure for both the axillary lymph node dissection and the sentinel lymph node biopsy. Although the risk of lymphedema is lower after a sentinel lymph node biopsy than with an axillary lymph node dissection, it can still occur (estimated 5-7%).

To perform ARM, 2.5 ccs of 1% isosulfan blue dye (10 g/L concentration) will be injected subcutaneously in the volar surface of the ipsilateral upper extremity at the bicipital sulcus after induction of anesthesia. Participating surgeons at UW Health have experience performing ARM with isosulfan blue dye. During the axillary surgery, identification of lymphatics will be attempted. If lymphatics are visualized in the surgical field, lymphatics draining the arm that do not also have crossover breast drainage will be spared or reapproximated. Importantly, the ARM procedure does not influence the extent of an axillary surgery, as it does not determine whether or not lymph nodes are involved with cancer. Rather, the dye maps the pathway of arm lymphatic flow so that these lymphatics can potentially be spared during an axillary surgery. The breast surgeon will use the blue dye to guide clinical decision-making for the ARM procedure.

##### Research Procedures:

ARM mapping with ICG fluorescence using the Asimov Platform: The research procedures will include using ICG fluorescence for the ARM mapping. OnLume will provide a sterile drape designed specifically for the OnLume Asimov. 25 mg of ICG and 10 mg Sterile Water will be dispensed for injection by UW Health pharmacy. Before the image acquisition of each patient, ICG will be reconstituted under sterile conditions with Sterile Water for Injection(2.5 mg/1 ml). Shake the vial gently to dissolve. Reconstituted ICG must be used within 6 hours after reconstitution. The total dose of dye will be kept below 2 mg/kg of patient body weight.

ICG dosing described in the literature has varied significantly (Table 1). A total dose of 1 ml (2.5 mg) of ICG will be injected subdermally, in divided doses. 0.5 ml will be injected in the subcutaneous fat in the volar surface of the upper arm at the bicipital sulcus and 0.5 ml in the 2nd interdigital space. The two injection protocol follows the published experience by Abacci, et al. with the goal to improve ICG's circulation through the lymphatic vessels. The upper arm injection will be performed within 1 cm of the isosulfan blue dye injection and will occur after induction of anesthesia. At least two minutes of massage will be performed to promote upper limb lymph flow. Visualization of the lymphatics using the Asimov Platform will be attempted

**Table 1. Summary of Injections Methods for ICG in ARM Procedure**

Author	Dose of ICG injected	Injection Location
Noguchi 	0.1 ml (0.25 mg)	Inner wrist
Noguchi 	0.1 ml (0.25 mg)	Inner wrist
Ikeda 	0.5-1ml (5 mg)	Upper inner arm
Ikdea 	0.5-1 ml (5 mg)	Upper inner arm
Sakurai 	0.15 ml	Interdigital area
Foster 	0.5-3 mg/ml	Upper arm
Ma 	1 ml (0.5 mg/ml)	Upper arm
Yuan 	1 ml (2.5 mg)	Upper arm
Abacci 	1 ml (2.5 mg/ml) in divided doses	Upper arm, 2nd interdigital space

Subjects will receive fluorescence imaging using the Asimov Imaging Platform. Beginning at the time of ICG injection, image and video capture of white light reflectance and fluorescence will be collected.

Impact on clinical care of the ICG mapping: The objective of this study is to evaluate the feasibility of using ICG fluorescence *through the Asimov Imaging Platform*. Compared to other platforms, the Asimov Imaging Platform allows real time imaging without altering ambient light. The presence of ICG fluorescence visualized lymphatics will be documented per the research protocol, but will not be used to influence surgical decision making.

#### 4.5. Data Collection

Operative data related to ARM: For each case, we will also assess whether blue dye identified lymphatics were visualized (yes/no) in the nodal basin and whether the blue lymphatic was spared (yes/no). We will also assess whether ICG identified lymphatics were visualized (yes/no) in the nodal basin and whether the ICG lymphatics were spared (yes/no). Surgical decision making will be guided by the blue dye only and the ICG fluorescence will not be considered. However, we will still document whether or not the ICG fluorescent lymphatics were spared. We will assess whether intact lymphatic channels were present at the completion of the axillary surgery via both techniques (yes/no/not assessable). We will record time at start of case, any fluorescent imaging, and completion of axillary surgery (defined as removal of last lymph node).

Chart review demographics and tumor characteristics: We will record other limited demographics about the patient including: Age, race/ethnicity, BMI, type of axillary surgery, type of breast surgery, receipt of neoadjuvant systemic therapy, prior axillary surgery, prior receipt of radiation, clinical and pathologic cancer stage (tumor size and lymph node status), and receptor status (estrogen receptor, progesterone receptor, her2neu). We will record the number of lymph nodes removed. We will indicate whether removed lymph nodes had radiotracer, blue dye, or fluorescence. For patients undergoing SLN biopsy, this will allow us to assess whether the SLN is the same as the ARM identified node. We will evaluate for any additional axillary surgeries or complications related to axillary surgery (infection, lymphedema) until 1 year post-surgery. We will document receipt of post-operative radiation.

Technical data related to ICG fluorescence imaging: Beginning at the time of ICG injection, image and video capture of white light reflectance and fluorescence will be collected. Following the operation, post-processing will be conducted to elucidate injection technique superiority. Physicians will confirm software-assisted lymphatic labels in the video and measure vessel diameters.

We will use quantitative fluorescence to define optimal image acquisition parameters. In order to elucidate injection technique superiority, the critical image acquisition parameters that provide surgeons detectable contrast (CNR) of post-injection time, and fluorescence signal retention of lymphatic vessels will be measured.

#### **4.6. Analysis Plan:**

1. Aim 1: To determine the feasibility of using ICG fluorescence for axillary reverse mapping through the Asimov Imaging Platform by comparing lymphatic visualization using blue dye (standard of care) versus ICG fluorescence imaging: Given the increased optical penetration with the ICG lymphatics, we anticipate greater visualization with the ICG. The proportion of cases where blue dye visualized lymphatics can be seen after 5 minutes post-injection will be reported along with the corresponding 95% confidence interval, which will be constructed using the Wilson score method. The same proportion will be reported for the ICG lymphatics. Comparisons between visualization of lymphatics by blue dye versus ICG fluorescence imaging will be made using test of two proportions. We will also compare whether lymphatics were able to be spared and whether intact lymphatic channels were able to be confirmed via both techniques. We will also generate descriptive statistics of patient characteristics associated with visualization of lymphatics with each approach to explore clinical scenarios when an approach may be less effective. For comparisons, the blue dye is considered the standard of care comparison.
2. Aim 2: To define optimal image acquisition parameters of using ICG fluorescence through the Asimov Imaging Platform for axillary reverse mapping.  
Aim 2a. To define dynamic range of ICG fluorescence signal in lymphatic vessels and background: Imaging acquisition parameters generated from image snapshots and videos will be summarized using standard descriptive statistics, including means, standard deviations, medians and interquartile ranges to characterize the dynamic range of ICG fluorescence signal in lymphatic vessels and the background. Nonlinear regression analyses will be conducted to statistically model CNR as a function of ICG dose and time.  
Aim 2b. To assess image contrast as a function of ICG dose and time post injection: Image contrast (CNR) will be measured for these lymphatics vessels and a time-curve will be developed that demonstrate the change in contrast over time. The magnitude of fluorescence signal retention of ICG in the lymphatic vessels, which is a function of both pharmacokinetics/pharmacodynamics of ICG and the sensitivity of the imaging platform, will be measured. Detectable contrast is defined by the Rose criterion: CNR>3.

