#### **4.7. Sample Size:**

We will plan to enroll approximately 0-20 patients undergoing SLN biopsy and 0-15 patients undergoing an ALND for a total of about 25 patients. The proposed total sample size is sufficient to generate descriptive statistics with an adequate level of precision. Specifically, the proportion of cases where lymphatics can be seen after 5 minutes post-injection will be estimated with a standard error of less than 12% and the corresponding 95% confidence interval will be no wider than 40%.

No power calculation is calculated for this feasibility study.

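### Aim 1 compares two dyes given to the same patients with a two-proportion test that, as ordinarily understood, assumes independent groups

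*Combined protocol and SAP*

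**What the plan says.** Section 4.1 describes a single cohort. All patients have axillary reverse mapping with isosulfan blue, and "Patients will also receive ICG injection with visualization through the Asimov Imaging Platform to allow comparison of blue dye versus ICG lymphatic identification". The Research Procedures text in section 4.5 puts the two upper-arm injections side by side: "The upper arm injection will be performed within 1 cm of the isosulfan blue dye injection".

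The Data Collection section records one binary result per dye per patient: "For each case, we will also assess whether blue dye identified lymphatics were visualized (yes/no) in the nodal basin", and likewise "We will also assess whether ICG identified lymphatics were visualized (yes/no) in the nodal basin".

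For Aim 1, section 4.6 plans a proportion with a 95% Wilson interval for each dye. It then states: "Comparisons between visualization of lymphatics by blue dye versus ICG fluorescence imaging will be made using test of two proportions". It adds: "We will also compare whether lymphatics were able to be spared and whether intact lymphatic channels were able to be confirmed via both techniques", without naming a test for those two outcomes. The documents do not mention McNemar's test, matching, discordant cases, a paired difference or within-patient correlation.

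Section 4.7 bases the sample of about 25 on the precision of a single proportion and says: "No power calculation is calculated for this feasibility study".

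**The concern.** The unit of comparison is the patient, who acts as her own control. An analyst who follows section 4.6 literally would compare 25 blue-dye results with 25 ICG results as if they came from 50 different people. The standard error would then leave out the covariance between the two results in one patient.

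Two things are at stake. First, the p-value does not have its nominal error rate. If some axillae are easy or difficult for both dyes (positive correlation), the test rejects too rarely. If one dye tends to succeed where the other fails (negative correlation), it rejects too often. Second, two separate totals do not report what a surgeon most wants to know from this design: in how many patients ICG showed a channel that blue dye missed, and in how many the reverse.

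This is the only test named for Aim 1, and Aim 1 is defined as this comparison. The Wilson interval for each dye is sound and is not in question.

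**Working it through.** **The plan's own figure.** Section 4.7 promises a standard error below 12% and a 95% interval no wider than 40%. At n = 25 the largest standard error is √(0.25/25) = 10.0%. The widest Wilson interval (12 or 13 of 25) is 2 × 1.96 × √(0.48 × 0.52/25 + 1.96²/(4 × 25²)) / (1 + 1.96²/25) = 36.5%. Both statements hold, but they concern one dye at a time. The plan gives no figure for the comparison.

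**Inputs.** From the documents: about 25 patients, so 25 pairs. Assumed, because the documents give none: two-sided 5% level, visualization rates, and within-patient correlation phi. The two-proportion test is taken as the pooled z test.

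**Why the test goes wrong.** If both dyes have rate p, the true variance of the difference in proportions is 2p(1−p)(1−phi)/n. The unpaired test uses 2p(1−p)/n. The real critical value is therefore about 1.96/√(1−phi):

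- phi = −0.2: 1.79, approximate type I error 7.4%
- phi = 0.3: 2.34, approximately 1.9%
- phi = 0.5: 2.77, approximately 0.6%

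**Exact type I error.** All possible paired 2x2 tables for 25 pairs were enumerated with multinomial probabilities. With both rates at 70%:

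| phi | unpaired z | mid-p McNemar |
|---|---|---|
| −0.2 | 7.7% | 4.4% |
| 0 | 5.4% | 4.2% |
| 0.3 | 2.2% | 3.7% |
| 0.5 | 0.8% | 2.7% |

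Over common rates of 50% to 80% and phi from −0.2 to 0.5, the z test ranges from 0.8% to 9.3% and mid-p McNemar from 1.7% to 4.7%. With both rates at 70%, the z test at phi −0.2, 0.3 and 0.5 gives 7.8%, 2.1% and 0.7% with 20 pairs, and 7.4%, 2.0% and 0.6% with 35. The pattern does not depend on exactly 25 being enrolled.

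**Power with 25 pairs (unpaired z against mid-p McNemar).**

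| phi | blue 60%, ICG 85% | blue 70%, ICG 90% |
|---|---|---|
| 0 | 53% vs 47% | 45% vs 38% |
| 0.3 | 54% vs 62% | 44% vs 48% |
| 0.5 | 54% vs 77% | 41% vs 57% |

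The largest possible phi is 0.514 for the first pair of rates and 0.509 for the second.

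**Worked example.** Suppose blue dye succeeds in 15/25 and ICG in 21/25, a difference of 24 points. The pooled rate is 36/50 = 0.72, so z = 0.24/√(0.72 × 0.28 × 2/25) = 0.24/0.127 = 1.89 and p = 0.059. Five pairings give these same totals:

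| ICG only / blue only | unpaired p | mid-p McNemar p | Tango 95% CI (points) |
|---|---|---|---|
| 6 / 0 | 0.059 | 0.016 | 7.5 to 43.4 |
| 7 / 1 | 0.059 | 0.039 | 2.2 to 45.0 |
| 8 / 2 | 0.059 | 0.065 | −0.9 to 46.5 |
| 9 / 3 | 0.059 | 0.092 | −3.4 to 47.9 |
| 10 / 4 | 0.059 | 0.118 | −5.6 to 49.3 |

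For 6/0 the mid-p value is 2 × (1/64) − 1/64 = 0.016. The same totals can support different conclusions, and the planned test cannot separate them.

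**The case against.** The plan does not say independent, z or chi-square, so it could be called underspecified rather than wrong. That is fair as to intent. But the usual reading of the phrase is the independent-samples test, and the same paragraph is specific enough to name the Wilson method, so the wording needs changing either way.

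It is also true that the unpaired test is not blind to discordance. The difference between the totals equals ICG-only minus blue-only cases, so both tests share a numerator; what the unpaired test gets wrong is the variance.

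Positive correlation is plausible, because anatomy, surgeon and field are shared. The z test is then conservative and the cost is power, not false positives. The 9.3% figure needs negative correlation with both rates at 50%, and nothing in the documents points to negative correlation. At phi = 0 the z test has more power than mid-p McNemar, with type I error slightly above nominal. The argument for a paired test is therefore correct error control and fuller reporting, not guaranteed power.

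Mid-p is not the only acceptable choice. Asymptotic McNemar held 4.2% to 4.9% at rates of 50% to 80%, and at 60% vs 85% had power of 64% against 62% for mid-p at phi = 0.3. It also agrees with the Tango interval by construction, whereas mid-p can disagree: with 4/0 discordant cases the Tango interval excludes zero but mid-p gives p = 0.0625. The choice between them is secondary to the pairing.

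Finally, section 4.6 plans descriptive statistics on when each approach may do less well. This helps, but it does not replace the paired table.

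**Conclusion.** The concern holds. The design yields matched pairs, and the only named comparison, read in its ordinary meaning, ignores the matching. Under the assumed rates and correlations, true type I error lies between 0.8% and 9.3% at a nominal 5%, and the unpaired test gains nothing from positive correlation. The size and direction of the error in this trial cannot be known in advance, because the documents give neither rates nor a correlation.

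This should be fixed, but the consequence is limited. The study is a feasibility study without a power calculation or a decision rule tied to the p-value, ICG findings do not guide surgery, and the per-dye estimates and the sample-size statement are unaffected. No wrong test is alleged for sparing or intact channels, since none is named there.

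**What to change.** In section 4.6, replace the two-proportion test for visualization with wording such as: *Visualization by blue dye and ICG will be compared within patients using the mid-p McNemar test. The paired 2x2 table (both, ICG only, blue only, neither) and the paired difference with a Tango score 95% confidence interval will be reported.* Keep the Wilson interval for each dye. Asymptotic McNemar is an acceptable alternative and matches the Tango interval. If mid-p is kept, say which result takes precedence should the two disagree. Exact McNemar is less attractive at this size: at 60% vs 85% its power is 37% at phi = 0 and 49% at 0.3, against 53% and 54% for the z test.

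For sparing and intact channels, state whether a test is planned and, if so, make it paired. The not-assessable category is recorded only for intact channels. There, restrict the comparison to patients assessable by both techniques and report how many were not.

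One related point needs tidying: section 4.6 defines visualization as seen after 5 minutes post-injection, while the Data Collection section lists nodal-basin yes/no results without a time. Make the two definitions agree and apply them equally to both dyes.

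The cost is a few sentences of analysis text. Nodal-basin yes/no results for both dyes are already to be collected in every case, and no extra patients are needed.
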